4.2 Immune Response

To evaluate the magnitude of peripheral immune response over time as determined by the following:

- Peripheral PAP-and PA2024 specific T cell immune response to sipuleucel-T over time via T cell stimulation index from a proliferation assay.
- T cell interferon-gamma (IFN- γ) enzyme-linked immunospot (ELISPOT) response to PA2024 and PAP
- Humoral response by enzyme-linked immunosorbent assays (ELISA) to PA2024 and PAP
- Chemokine and cytokine production via fluorescent immunoassay (MesoScale Discovery assay system).

The PAP and PA2024 IFN γ ELISPOT response over time will be compared between the Concurrent Arm and the Sequential Arm, beginning with the immune sample taken at the baseline, using a repeated measurement mixed model analysis stratified by screening PSA levels and screening lactate dehydrogenase. The unit of analysis will be the background subtracted counts, computed as the median count of 3 wells exposed to antigen minus the median count of 3 wells exposed to media alone. The background subtracted counts will be ranked prior to analysis. The model will include treatment and visit as fixed effects as well as treatment by visit interaction, subject as random effect, and the two stratification factors at randomization as covariates. Visit will be considered as a categorical variable for the modeling. Several variance-covariance structures will be investigated to determine which model fit is best based on the model with the lowest Bayesian Information Criteria (BIC). Variance-covariance structures that will be investigated are unstructured (UN), auto-regressive (1) AR(1), heterogeneous autoregressive (1) (ARH (1)), compound symmetry (CS), and heterogeneous compound symmetry (CSH). Comparisons between the treatment arms at specific timepoints visits will be made using a linear contrast statement. A proper transformation (such as log-scale or rank transformation) will be applied if the data are not normally distributed. A secondary analysis of this endpoint will be based on a categorical response/no response basis. Categorical response will be defined on the basis of a threshold value determined from PA2024 ELISPOT background subtracted counts measured at baseline that ensures a sufficiently low false positive rate (i.e., 5% or less). The two treatment arms will be compared using a Fisher's exact test for a response at any time point post-baseline and by time point.

The T cell proliferation in response to PAP and PA2024, and PAP and PA2024 humoral responses of both arms will be compared using methods as described for the PA2024 ELISPOT response for IFN- γ . The unit of analysis for the T cell proliferation data is the stimulation index, defined as the median ^3H uptake of 3 wells exposed to antigen divided by the median ^3H thymidine uptake of 3 wells exposed to media. The stimulation index will be log-transformed prior to analysis. The unit of analysis for the humoral response data is the antibody titer, which will be log-transformed prior to analysis. In addition, the responder rate will be summarized by time point for the data generated from the proliferation assays, ELISPOT, and ELISA. A responder at a time point is a subject with a post-baseline result at the time point exceeding the 95th percentile at baseline.

AIM-V Cytokine data will be collected after each infusion of sipuleucel-T. Each cytokine parameter over time will be compared between the Concurrent Arm and the Sequential Arm, using a repeated measurement mixed model analysis. The same modeling strategy as outlined for PA2024 ELISPOT response for IFN- γ will be applied to the AIM-V cytokine data. Comparisons between treatment arms at specific time points will be made using a linear contrast statement. The data will be analyzed on a log-scale with a count of 1 added prior to taking the log so that the log will always be defined. Serum cytokine data will be analyzed in a manner similar to the AIM-V cytokine data.

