## **8.4 Endpoints**

### **8.4.1 Primary Endpoint(s)**

The primary endpoint is peripheral PA2024-specific T cell immune response to sipuleucel-T over time as measured via a T cell stimulation index from a proliferation assay. This endpoint was selected because it has demonstrated the highest signal to noise ratio of all the T cell assays Dendreon has evaluated in prior studies of sipuleucel-T (data on file).

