3.4 Data Rules

- *Study Day* = [(visit date) – (date of first infusion [Day 0])]. If the infusion does not occur, Day 0 will be the date of the first leukapheresis, unless it fails, in which case, Day 0 will be the date of registration.
- *Baseline*: baseline is defined as the value closest to but prior to the randomization data.
- *Change from baseline*: change from baseline is the post-baseline value minus the baseline value.
- *Percent change from baseline*: percent change from baseline is calculated as $100 \times (\text{post-baseline value} - \text{baseline value}) / \text{baseline value}$. If the baseline or post-baseline value is missing, then the change from baseline and percent change are set to missing. If the baseline value is zero and the post-baseline is non-zero, then the percent change from baseline is set to missing. If the baseline value is zero and the post-baseline value is also 0, then the percent change from baseline is set to 0.
- *Partial Dates*: Dates missing the day, month and year and the day and month will not be imputed. However, if the month and year are present, the day may be set to the 15th of the month or to a date consistent with a more conservative approach to the analysis of the data point.
- *Missing event or censor date*: If the date of an event or the date of censoring is missing for a time-to-event variable, the last known study date will be used. Subjects who prematurely discontinue from the study before having the event will be censored at their last known alive date.

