4.3 PSA

PSA data, including change from baseline and percent change from baseline, will be summarized descriptively by treatment arm at each time point. For each time point where change from baseline is evaluated for continuous variables, descriptive statistics will be displayed for the values at baseline, values at the time point, values for change from baseline, and percent change from baseline at the time point for the set of subjects who have data at both baseline and the time point being assessed. Additionally, the maximal percent decline of serum PSA from baseline at any time point will be summarized using waterfall plots and will be compared between the treatment groups using a Wilcoxon test. Baseline will be defined as the pre-randomization PSA value. The percent of subjects with a 50% or more maximal decline in PSA at any post-baseline time point will be compared between the treatment arms using a Fisher's exact test.

Time to PSA progression will be compared between the treatment arms using a Cox regression model with terms for treatment, baseline PSA (logarithm scale), and baseline LDH (logarithm scale) in the model based on the ITT population. The estimated HR of the treatment effect and its 2-sided, 95% CI, using the sequential arm as the denominator will be provided. The percentage of subjects free of PSA progression with an associated 95% CI at landmark time points such as 6 and 12 months will be provided by treatment arm as well as pooled over treatment arms using the Kaplan-Meier method.

Time to PSA progression is defined as: 1) the time from randomization to PSA progression, and 2) the time from first enzalutamide treatment to PSA progression. Those subjects who do not experience PSA progression will be censored in the analysis at the date of their last PSA assessment. PSA progression, based on the randomization date (i.e., definition 1) will be defined for those subjects

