4.4 Overall survival

Overall survival is defined as the time from randomization to death due to any cause. Subjects will be followed for survival for 3 years from the date of randomization. Those subjects alive at study end will be censored in the analysis at the day of their last documented visit or contact date. Overall survival time will be calculated as follows:

- For subjects who died prior to the study end:
 - Survival time (days) = [(death date) – (randomization date) + 1]
- For subjects who did not die prior to the study end or whose death status is unknown:
 - Survival time (days) = [(last contact date) – (randomization date) + 1]

Overall survival will be compared between the two arms using a stratified log-rank test. The estimated adjusted hazard ratio of the treatment effect and its 2-sided 95% CI, using the sequential arm as the reference group, will be generated using a Cox regression model adjusted for baseline PSA (natural log scale) and baseline LDH (natural log scale). Median survival and survival rates at specific time points will be estimated for each treatment arm using the Kaplan-Meier method, with corresponding 95% CIs.

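### SAP 4.2 enters the pre-randomization immune sample as an outcome visit: the arm comparison is not adjusted for it, and any overall arm effect is diluted by one tenth on the log scale

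*SAP*

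**What the plan says.** SAP 4.2 describes the model for the ELISPOT counts and then extends it. The comparison runs "beginning with the immune sample taken at the baseline, using a repeated measurement mixed model analysis". Fixed effects are arm, visit (categorical) and arm by visit, with subject as a random effect. The only covariates are "the two stratification factors at randomization as covariates". Arm contrasts at individual visits are planned. Proliferation and "humoral responses of both arms will be compared using methods as described for the PA2024 ELISPOT response", with stimulation index and titre on the log scale.

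PA2024 proliferation matters most here. Protocol 8.4.1 states: "The primary endpoint is peripheral PA2024-specific T cell immune response to sipuleucel-T over time".

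SAP 3.4 places baseline before randomization: "baseline is defined as the value closest to but prior to the randomization data" (presumably meaning the date). SAP 1 lists ten immune samples: screening, preleukapheresis 2 and 3, and weeks 6, 10, 14, 20, 26, 40 and 52. The baseline immune value has one other use, setting responder cut-offs: "A responder at a time point is a subject with a post-baseline result at the time point exceeding the 95th percentile at baseline".

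The overall arm effect appears elsewhere. Protocol 8.5.3 bases the formal test on the arm term unless the arm-by-visit interaction has p < 0.05, and reports the effect as a ratio with a 95% CI. It does not say whether baseline is a modelled visit. SAP 4.2 has no such rule, but proposed tables 14.2.12.2 and 14.2.12.4 are to estimate treatment and visit effects for proliferation.

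**The concern.** A sample taken before randomization cannot show a response to sipuleucel-T or an effect of enzalutamide timing. Entering it as an outcome visit, with the arm difference there left free, has two consequences.

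- The by-visit contrasts do not use the subject's starting value, although the sample is already collected and enrolment was cut from 100 to 52 subjects.
- Any arm effect averaged over all visits includes one visit at which treatment can have had no effect, so the overall ratio is pulled toward 1.

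A third consequence is conditional. If the Protocol 8.5.3 interaction rule is applied to the SAP model, a zero difference at baseline followed by a constant difference afterwards is itself an arm-by-visit interaction.

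**Working it through.** **Inputs.** From Protocol 8.2 and SAP 3.1: 2-fold difference, d = ln 2 = 0.693; CV 1.25, so the log-scale SD is s = sqrt(ln(1 + 1.25²)) = 0.970 and s² = 0.941; two-sided 0.05; enrolment 25 and 27. From SAP 1: one baseline and nine post-baseline samples. Assumed: all 52 evaluable, the same CV at every visit, correlation r = 0.5 between post-baseline visits, and baseline to post-baseline correlation r0 of 0 to 0.5.

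**Stated powers.** A two-sample comparison of log means (noncentral t) gives 90.6% at 43 per arm (stated 90%) and 69.7% at 25 per arm (stated about 70%). Both reproduce. They are single-visit calculations without baseline adjustment, so this point does not touch them.

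**By-visit contrasts.** At 25 per arm with complete data and equal correlations of 0.3, 0.5 or 0.7, generalized least squares with a free baseline arm difference gives a post-baseline contrast SE of 0.2744. The plain two-sample SE is the same: 0.970 × sqrt(2/25) = 0.2744. Baseline contributes nothing. As a covariate it multiplies the variance by 1 − r0². At 25 and 27 the unadjusted SE is 0.970 × sqrt(1/25 + 1/27) = 0.269 and power is 71%. Adjusted:

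- r0 = 0.1: variance × 0.99, power 72%
- r0 = 0.3: variance × 0.91, power 75%
- r0 = 0.5: variance × 0.75, power 83%

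**Overall arm effect: estimate.** The type III arm effect is the equal-weight mean of the visit differences. With a zero difference at baseline and a constant 2-fold difference afterwards, it estimates 2^(9/10) = 1.87 (2^(10/11) = 1.88 if the post-treatment sample in Protocol Table 1 is also modelled). If the 2-fold difference holds only at the four post-baseline visits up to week 10, about when the sequential arm starts enzalutamide, the average is 2^(4/10) = 1.32 with baseline and 2^(4/9) = 1.36 without.

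**Overall arm effect: power and precision.** The variance of a subject's post-baseline mean is Vpost = s²(1 + 8r)/9 = 0.941 × 5/9 = 0.523. As written, the effect is 0.9d and the variance is (81 Vpost + s² + 18 r0 s²)/100. With the covariate, the effect is d and the variance is Vpost − r0² s². Degrees of freedom are 50, or 49 with the covariate. The CI multiplier is exp(t × sqrt(variance × (1/25 + 1/27))).

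| r0 | Variance, as written / covariate | Power, as written / baseline dropped / covariate | 95% CI multiplier, as written / covariate |
|---|---|---|---|
| 0 | 0.433 / 0.523 | 92 / 92 / 92% | 1.44 / 1.50 |
| 0.1 | 0.450 / 0.513 | 91 / 92 / 93% | 1.45 / 1.49 |
| 0.3 | 0.484 / 0.438 | 89 / 92 / 96% | 1.47 / 1.45 |

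For a 1.5-fold effect, as written against covariate is 50/51, 49/52 and 46/58%. If baseline CV were 0.69, the low end of the by-visit range in Protocol 8.2, as-written power for a 2-fold effect at r0 = 0.3 would be 90% instead of 89%.

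**Interaction rule, if applied.** For a constant 2-fold effect, the noncentral F (9 and 450 df) has noncentrality 4.26, 4.89 and 6.94 at r0 = 0, 0.1 and 0.3. The interaction is then significant in 24%, 27% and 39% of trials, against 5% with post-baseline visits only. In simulation (20,000 trials per cell), detection by the arm effect, or by any nominal post-baseline contrast once the interaction is significant, is 92% as written and 93% post-baseline only at each of these correlations.

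**The case against.** **Nothing the SAP names is distorted.** SAP 4.2 specifies by-visit contrasts, and these are undiluted. The arm-effect ratio and the interaction rule are in Protocol 8.5.3, which does not make baseline a visit. This stands: the dilution and the interaction effect depend on combining the two documents, although the table titles make an overall estimate likely.

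**The gain may be small.** Exclusion 4.2.7 rules out prior sipuleucel-T, so baseline precedes any exposure and may correlate weakly with later values. At r0 of 0 to 0.1 the power gain is 0 to 2 points. This also stands.

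**A constant effect to week 52 is doubtful.** Both arms are scheduled for enzalutamide from about week 10. With an early effect only, averaging over late visits does most of the dilution (2.00 to 1.36), and baseline adds little (to 1.32).

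A reader might infer four stronger things that the documents and figures do not support:

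- *That the baseline sample is unused.* It sets the responder cut-offs, and as part of the outcome vector it informs the likelihood when later visits are missing.
- *That the overall ratio is estimated less precisely as written.* At r0 of 0 to 0.1 its interval is narrower (1.44 to 1.45 against 1.50 to 1.49), but centred on a diluted quantity.
- *That the interaction rule costs much detection.* It does not in the cases above. At equal correlations of 0.5 and 0.6 between all visits, detection as written is slightly higher (94 against 93%, and 93 against 89%).
- *That the SAP breaks its own precedent.* The time-to-PSA-progression model is fitted "with terms for treatment, baseline PSA (logarithm scale), and baseline LDH (logarithm scale) in the model" and the survival model adjusts for the same two variables, but these underlie the stratification factors that the immune model already includes.

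**Conclusion.** The point holds as one of efficiency and interpretation. SAP 4.2 models a pre-randomization sample as an outcome and does not adjust the arm comparison for it. The firm part is that, with complete data, the planned by-visit contrasts gain nothing from baseline. What adjustment would add depends on an unknown correlation: from nothing at 0 to 12 points of single-visit power at 0.5 (71% to 83%). The conditional part is that an overall arm effect from this model would turn a constant 2-fold effect into about 1.87, with 92/92, 91/93 and 89/96% power (as written / covariate) at baseline correlations 0, 0.1 and 0.3.

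These figures assume 25 and 27 evaluable subjects, CV 1.25, correlation 0.5 between post-baseline visits and no arm difference at baseline. No error inflation is involved, SAP 4 makes all tests exploratory, and the stated sample-size powers stand.

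**What to change.** In SAP 4.2, use only post-baseline visits as outcomes. Add the baseline value of the same assay (log stimulation index, log titre, ranked ELISPOT count) as a covariate beside the two stratification factors. Define any overall arm effect, and any arm-by-visit test, over post-baseline visits, and say whether the post-treatment sample is one of them. Leave the AIM-V cytokines as they are, since they are collected after each infusion.

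Prefer the covariate to a model that keeps baseline as an outcome and constrains the arm means to be equal there. The immune response population (SAP 3.2.1) is selected on treatment received after randomization, so randomization does not guarantee equal baselines in it.

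The cost is a change of SAP wording and one degree of freedom with a single baseline slope. Subjects with a missing baseline assay drop out of the covariate model, because SAP 3.3 does not impute; their number should be reported. No new samples are needed.

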#### **8.4.2 Secondary Endpoint(s)**

Immune responses over time for ELISPOT and ELISA are secondary endpoints as are peripheral PAP-specific T cell immune response to sipuleucel-T over time via a T cell stimulation index from a proliferation assay, and cytokine production by Luminex assay. Additionally, responder analyses by time point will be performed for the data generated from the proliferation assays, ELISPOT, and ELISA. A positive response will be defined as having a post-baseline result exceeding a threshold value, determined on the basis of baseline and historical sipuleucel-T data, that ensures a sufficiently low false positive rate (i.e., 5% or less) for each immune response parameter. The threshold will be antigen and assay dependent.

Time to PSA progression is defined as: 1) the time from randomization to PSA progression, and 2) the time from first enzalutamide treatment to PSA progression. Those subjects who do not experience PSA progression will be censored in the analysis at the date of their last PSA assessment. PSA progression, based on the randomization date (i.e., definition 1) will be defined for those subjects who experience a decline in PSA compared to baseline as the date that a 25% or greater increase in PSA and an absolute increase of 2 ng/mL or more from the nadir is documented, which is confirmed by a second value obtained 3 or more weeks later (Scher 2008). For those subjects who do not experience a decline in PSA compared to baseline, PSA progression is defined as the date a 25% or greater increase from the baseline value along with an increase in absolute value of 2 ng/mL or more after 12 weeks of enzalutamide treatment (Scher 2008). PSA progression based on the first enzalutamide treatment (i.e., definition 2) will be defined in a similar manner except the most recent PSA value prior to the first enzalutamide treatment will be used as the baseline value.

PSA progression time, based on the randomization date, will be calculated as follows for those subjects with PSA progression:

$$\text{Progression time (days)} = [(\text{PSA progression date}) - (\text{randomization date})] + 1.$$

PSA progression time, based on the randomization date, will be calculated as follows for subjects who are censored:

$$\text{PSA progression time (days)} = [\text{last PSA assessment date} - (\text{randomization date})] + 1.$$

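### SAP 4.2 takes the ELISPOT responder threshold from PA2024 baseline counts only, contrary to the protocol's antigen-specific rule, so the 5% false-positive limit is not assured for PAP

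*SAP*

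**What the plan says.** SAP 4.2 introduces the mixed-model comparison of ELISPOT counts for PAP and PA2024 together. It continues: "A secondary analysis of this endpoint will be based on a categorical response/no response basis". Response is then defined by a "threshold value determined from PA2024 ELISPOT background subtracted counts measured at baseline", chosen to keep the false-positive rate at 5% or less. The arms are compared on this basis: "The two treatment arms will be compared using a Fisher's exact test for a response at any time point post-baseline and by time point".

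The next paragraph of 4.2 turns to proliferation and humoral responses and refers back to "methods as described for the PA2024 ELISPOT response". It then adds a by-visit responder summary for proliferation, ELISPOT and ELISA with its own rule: "A responder at a time point is a subject with a post-baseline result at the time point exceeding the 95th percentile at baseline".

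Protocol 8.4.2 bases the thresholds on baseline and historical sipuleucel-T data and asks for a "sufficiently low false positive rate (i.e., 5% or less) for each immune response parameter". It ends: "The threshold will be antigen and assay dependent". Protocol 8.5.3 compares response rates between arms by Fisher's exact test at each visit, for every assay and every antigen.

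**The concern.** A percentile of one variable's distribution does not fix how often another variable exceeds it. A cut-off calibrated on PA2024 baseline counts therefore carries no guarantee for PAP counts. ELISPOT response to PAP is a named secondary objective in both documents (section 2.2 of each), and the protocol plans a test on its responder rate.

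The two rules in SAP 4.2 add to the problem. For PA2024 they can coincide, since a baseline 95th percentile has a 5% exceedance rate. For PAP they differ unless the two antigens share a baseline 95th percentile. An analyst would have to choose between them, in an open-label study where immune summaries may be produced periodically (Protocol 8.6, SAP 4.7.1). At stake are the calibration and sensitivity of the PAP responder rate.

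**Working it through.** **Texts side by side, for PAP ELISPOT**

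- Protocol 8.4.2: own threshold for each antigen and assay; 5% or less for each parameter; baseline plus historical data.
- SAP 4.2, categorical analysis with Fisher test: threshold from PA2024 baseline counts; no PAP threshold.
- SAP 4.2, by-visit summary: 95th percentile at baseline; antigen not named; no mention of historical data.
- SAP 5: the ELISPOT responder table titles name no antigen, so they do not settle the matter.

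**Can the 5% be reproduced?** It is a design target. Neither document gives a baseline ELISPOT distribution for either antigen, so it cannot be derived from the plan's inputs. By definition, a cut-off at an antigen's own baseline 95th percentile gives 1 − Φ(1.645) = 5.0% per time point for that antigen.

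**What happens to PAP under the PA2024 cut-off?** Assume a scale on which both baseline distributions are normal. Let *s* be the PAP mean minus the PA2024 mean, in PA2024 SDs, and *r* the ratio of the PAP SD to the PA2024 SD. Both are assumptions. Then

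P(PAP exceeds cut-off) = 1 − Φ((1.645 − *s*)/*r*).

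With *r* = 1:

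- *s* = −1: 1 − Φ(2.645) = 0.4%
- *s* = −0.5: 1 − Φ(2.145) = 1.6%
- *s* = 0: 1 − Φ(1.645) = 5.0%
- *s* = +0.5: 1 − Φ(1.145) = 12.6%
- *s* = +1: 1 − Φ(0.645) = 26.0%

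With *s* = 0:

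- *r* = 0.75: 1 − Φ(2.193) = 1.4%
- *r* = 1.25: 1 − Φ(1.316) = 9.4%
- *r* = 1.5: 1 − Φ(1.097) = 13.6%

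So the limit is met if PAP baseline counts are no higher and no more spread than PA2024 counts, at the price of lower sensitivity for PAP. Otherwise it can fail. A log scale would be a poor choice here, because the SAP's unit is antigen wells minus media wells, which can be zero or negative.

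**Effect on the between-arm test.** One cut-off serves both arms. If the arms have the same PAP distribution, both exceed any common cut-off with the same probability, so Fisher's exact test stays valid wherever the cut-off lies.

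**With a PAP-specific cut-off**, the rate returns to 5.0% per time point by definition, as for PA2024.

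**The case against.** The strongest reply is that the SAP already contains a usable PAP rule. The 95th-percentile rule covers proliferation, ELISPOT and ELISA. Stimulation indices, spot counts and titers have different units, so the percentile must be taken at least per assay. Taking it per antigen as well is the natural reading and agrees with the protocol. The back-reference to PA2024 also suggests that the threshold sentence was drafted for PA2024 alone, which would leave PAP undefined there rather than misjudged.

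Both readings are possible, and they rule out treating the literal one as settled. They do not remove the need for an edit. The 95th-percentile rule is attached to a descriptive summary, while the Fisher comparison sits with the PA2024 threshold. If that threshold was meant for PA2024 only, the categorical analysis has no PAP threshold beside it. Either way the text must change.

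A reader might go further and infer that the 5% rate fails for PAP, or that PAP responders will be over-counted. The documents do not support this: without baseline counts, neither the size nor the direction of any departure is known. Nor do they support an inference that the arm comparison is biased.

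It also stands that the stakes are modest. SAP 4.2 calls the analysis secondary, and SAP 4 makes all analyses descriptive or exploratory after the cut in sample size.

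**Conclusion.** The SAP's threshold sentence conflicts with the protocol's antigen-specific rule, and SAP 4.2 holds two ELISPOT responder rules that are not reconciled. On the literal reading the 5% limit is not assured for PAP. The assumed range above, from 0.4% to 26.0% for shifts of one SD either way with equal spread, shows only how strongly the rate depends on figures the documents do not give; it is not an estimate for this trial.

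The consequence is confined to the calibration and sensitivity of a secondary, exploratory PAP responder rate. It does not touch the proliferation endpoint or the validity of the between-arm Fisher test. The text should be corrected before the responder analyses are run.

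**What to change.** Replace both rules in SAP 4.2 with one definition, along these lines: *for each antigen and each assay separately, the threshold is the 95th percentile of that antigen's own baseline values, both arms pooled*. Delete the PA2024-only wording, and use this definition for both the by-visit summary and the Fisher tests. State whether historical sipuleucel-T data also enter the threshold, as Protocol 8.4.2 says, or record their omission as a departure from the protocol.

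The cost is about one sentence in the SAP and no new data. There is a small downside. With at most 52 subjects, 5% of the sample is 0.05 × 52 = 2.6, so a baseline-only threshold rests on the top two or three values. In a simulation with 52 normal baseline values, the false-positive rate of the empirical 95th percentile averaged 6.6%, with 90% of samples between 2.2% and 12.7%. This is a reason to settle the role of historical data explicitly.

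The definition controls the rate per time point only. For response at any of the nine post-baseline visits, 5% per visit would become 1 − 0.95⁹ = 37% if visits were independent, and less if they are correlated. That holds for either antigen and is a separate matter.
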